2.1 Schedule of Assessments

Trial Procedure/ Assessment	Screening ¹	MTX Run-in Period ²		Pegloticase + MTX Treatment Period ³ Day 1 through Week 24 EOT																	Optional Extension to Wk 48
				Week (± 3 d)																	
	Screening Visit	(-6 wks ± 3 d)	(-4 wks ± 3 d)	(-2 wks ± 3 d)	Day 1	Wk 2	Wk 4	Wk 6	Wk 8	Wk 10	Wk 12	Wk 14	Wk 16	Wk 18	Wk 20	Wk 21	End of Pegloticase Visit ⁴ (if applicable)	Wk 22	Wk 23	Wk 24/ EOT*	Wk 24 (± 3 d)
					Inf: 1	Inf: 2	Inf: 3	Inf: 4	Inf: 5	Inf: 6	Inf: 7	Inf: 8	Inf: 9	Inf: 10	Inf: 11	Within 2 wks following final infusion	Inf: 12			Inf: 13	
Informed consent	X																				
Enrollment					X																
Demographic data	X																				
Inclusion/exclusion criteria	X	X	X	X	X																
Medical/surgical history ⁵	X																				
Medication/substance use history ⁶	X																				
Chest x-ray	X																				
Physical examination ⁷	X			X	X	X	X	X	X	X	X	X	X	X	X	X	X	X	X	X	
Vital signs, height ⁸	X	X	X	X	X	X	X	X	X	X	X	X	X	X	X	X	X	X	X	X	
Weight ⁹	X				X												X		X	X	
Electrocardiogram ¹⁰	X																				
AE/SAE assessment ¹¹	X	X	X	X	X	X	X	X	X	X	X	X	X	X	X	X	X	X	X	X	

Trial Procedure/ Assessment	Screening ¹	MTX Run-in Period ²		Pegloticase + MTX Treatment Period ³ Day 1 through Week 24 EOT																		Optional Extension to Wk 48	
				Week (± 3 d)																			
	Screening Visit	(-6 wks ± 3 d)	(-4 wks ± 3 d)	(-2 wks ± 3 d)	Day 1	Wk 2	Wk 4	Wk 6	Wk 8	Wk 10	Wk 12	Wk 14	Wk 16	Wk 18	Wk 20	Wk 21	End of Pegloticase Visit ⁴ (if applicable)	Wk 22	Wk 23	Wk 24/ EOT*	Wk 24 (± 3 d)		
Concomitant medications	X	X	X	X	X	X	X	X	X	X	X	X	X	X	X	X	X	X	X	X	X	Inf: 13	
Document gout flares and intensity	X	X		X	X	X	X	X	X	X	X	X	X	X	X	X	X	X	X	X	X	Inf: 12	
CCI [REDACTED]		X			X			X			X			X		X		X		X		X	
HAQ-DI	X			X			X			X			X		X		X		X		X	X	
CCI [REDACTED]		X			X						X					X		X		X		X	
CCI [REDACTED]		X			X						X					X		X		X		X	
CCI [REDACTED]		X			X						X					X		X		X		X	
CCI [REDACTED]		X			X						X					X		X		X		X	
DECT ¹²		X									X					X		X		X		X	
MTX dosing calendar	X	X	X	X	X	X	X	X	X	X	X	X	X	X	X	X	X	X	X	X	X	X	
MTX dispensed ¹³	X	X	X	X	X	X	X	X	X	X	X	X	X	X	X	X	X	X*				X	
MTX dosing		Once weekly from Week -6 to Week 23 Visit, inclusive																					X
Folic acid Rx filled ¹⁴		Rx filled as needed																					X
Gout prophylaxis Rxs filled ¹⁵				Rxs filled as needed																			X

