	Screening Visit	(-6 wks ± 3 d)	(-4 wks ± 3 d)	(-2 wks ± 3 d)	Day 1	Wk 2	Wk 4	Wk 6	Wk 8	Wk 10	Wk 12	Wk 14	Wk 16	Wk 18	Wk 20	Wk 21	End of Pegloticase Visit ⁴ (if applicable)	Wk 22	Wk 23	Wk 24/ EOT*	Wk 24 (± 3 d)	
					Inf: 1	Inf: 2	Inf: 3	Inf: 4	Inf: 5	Inf: 6	Inf: 7	Inf: 8	Inf: 9	Inf: 10	Inf: 11		Within 2 wks following final infusion	Inf: 12			Inf: 13	
CCI [REDACTED]			X														X			X	X	

Table footnotes and abbreviations are presented on the last page.

	Optional Pegloticase + MTX Extension Period (Week 26 through Week 46)												Wk 48/ EOT/ET	30-Day Post- Treatment Follow-up Visit ²⁵	MTX Partner Pregnancy Follow-up
	Week (± 3 d)														
	Wk 26	Wk 28	Wk 30	Wk 32	Wk 34	Wk 36	Wk 38	Wk 40	Wk 42	Wk 44	Wk 46			~30 days after last pegloticase infusion or MTX dose (± 3 d)	~3 months after last MTX dose
Trial Procedure/ Assessment	Inf: 14	Inf: 15	Inf: 16	Inf: 17	Inf: 18	Inf: 19	Inf: 20	Inf: 21	Inf: 22	Inf: 23	Inf: 24				
Physical examination ⁷						X							X		
Vital signs ⁸	X	X	X	X	X	X	X	X	X	X	X				
Weight ⁹													X		
AE/SAE assessment ¹¹	X	X	X	X	X	X	X	X	X	X	X				
Concomitant medications	X	X	X	X	X	X	X	X	X	X	X				
Document gout flares and intensity	X	X	X	X	X	X	X	X	X	X	X				
CCI						X							X		
HAQ-DI						X							X		
CCI						X							X		
CCI						X							X		
CCI						X							X		
CCI						X							X		
DECT ¹²													X		
MTX dosing calendar	X	X	X	X	X	X	X	X	X	X	X				
MTX dispensed ¹³	X	X	X	X	X	X	X	X	X	X	X				
MTX dosing	Once weekly from Week 24 to the Week 47, inclusive														

	Optional Pegloticase + MTX Extension Period (Week 26 through Week 46)												Wk 48/ EOT/ET	30-Day Post- Treatment Follow-up Visit ²⁵	MTX Partner Pregnancy Follow-up
	Week (± 3 d)														
	Wk 26	Wk 28	Wk 30	Wk 32	Wk 34	Wk 36	Wk 38	Wk 40	Wk 42	Wk 44	Wk 46			~30 days after last pegloticase infusion or MTX dose (± 3 d)	~3 months after last MTX dose
Trial Procedure/ Assessment	Inf: 14	Inf: 15	Inf: 16	Inf: 17	Inf: 18	Inf: 19	Inf: 20	Inf: 21	Inf: 22	Inf: 23	Inf: 24				
Folic acid Rx filled ¹⁴	Rx filled as needed														
Optional gout prophylaxis Rx filled if needed ¹⁵	Rx filled as needed														
IR prophylaxis Rx filled ¹⁶	Rx filled as needed														
MTX compliance/ reconciliation	X	X	X	X	X	X	X	X	X	X	X	X			
IR prophylaxis ¹⁶ and compliance (Yes/No)	X	X	X	X	X	X	X	X	X	X	X				
Folic acid compliance (Yes/No)	X	X	X	X	X	X	X	X	X	X	X	X			
Optional gout flare prophylaxis compliance (N/A, Yes/No)	X	X	X	X	X	X	X	X	X	X	X	X			

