11. AEs/SAEs will be collected from the signing of the informed consent form until the 30-Day Post-Treatment Follow-up Visit. For each AE, the Investigator will be asked to record if the event was possibly an IR or anaphylaxis and if so, will be prompted to complete additional electronic case report forms. Females of childbearing potential will be asked to confirm if ovulation has occurred since the last dose of MTX. If the subject had not ovulated, a urine pregnancy test will be required.
12. The initial DECT scan will be performed after the Screening Visit, during the MTX Run-in Period and prior to the Day 1 Visit. Subsequent DECT scans may be performed ± 10 days from the scheduled visit date. Subjects who end pegloticase infusions prior to Week 24 should follow the scheduled time points and have a DECT scan at the End of Pegloticase (if applicable) and Week 24/End of Trial/ET Visits (detailed guidance is provided within the Imaging Manual). DECT will be carried out for all subjects where the site has the capability to conduct the test.
13. MTX will be dispensed and brought back to check compliance at each infusion visit. MTX should be injected 1 to 3 days prior to each pegloticase infusion; however, if a subject does not do so, MTX must be injected ≥ 60 minutes prior to each pegloticase infusion.

14. Subjects will take folic acid at a starting dose of 1 mg orally every day beginning Week -6 (preferably 2 days prior to the first dose of MTX) continuing until prior to the End of Pegloticase (if applicable) or until 1 week after the last pegloticase infusion for subjects who have not stopped pegloticase treatment. The folic acid dose can be increased or an alternative folate supplement can be used (see [Section 9.4.6.3.2.2](#) for detailed instructions).
15. Before a subject begins the Pegloticase + MTX Treatment Period, he or she must have been taking at least 1 standard gout flare prophylaxis regimen (i.e., colchicine and/or NSAIDs and/or low-dose prednisone \leq 10 mg/day) per protocol for \geq 1 week before the first dose of pegloticase and continue flare prophylaxis for at least 6 months per American College of Rheumatology guidelines ([FitzGerald et al, 2020](#)). Gout flare prophylaxis from Week 26 to the end of the trial will be administered, if needed, at the discretion of the Principal Investigator.

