During the Pegloticase + MTX Treatment Period, subjects will be instructed to inject MTX weekly on the same day each week, within 1 to 3 days prior to each pegloticase infusion (on the weeks when pegloticase is administered); however, if a subject does not do so, MTX must be injected ≥ 60 minutes prior to each pegloticase infusion. One additional weekly dose of MTX will be injected after the last pegloticase infusion for subjects who have not stopped pegloticase due to individual subject sUA discontinuation criteria. If the subject discontinues pegloticase due to the stopping rule or other reason, MTX and folic acid should also be discontinued.

After Day 1, if a subject becomes unable to tolerate MTX, the folic acid dose can be increased, an alternative folate supplement may be used and/or the MTX dosage may be reduced or discontinued based on pre-defined criteria (see [Section 9.4.6.3.2.2](#) for detailed instructions) and the subject may remain in the trial and continue pegloticase infusions. Every attempt should be made to re-start the MTX in subjects once their MTX-associated symptoms have improved or their laboratory tests have normalized.

The Investigator will review the subject clinical status and [CCI](#) ([Appendix 17.8](#)) at Week -6; prior to pegloticase infusion at the Week 24 and Week 36 Visits (subjects who may gain further benefit beyond 12 infusions and elect to receive pegloticase + MTX during the Optional Pegloticase + MTX Extension Period); and at the End of Pegloticase (if applicable) and Week 24 or 48/End of Trial/Early Termination Visits.

After the Week 24 or 48 Visit (or End of Pegloticase Visit [if applicable]) or upon pegloticase discontinuation, subjects should resume regular care for gout per the judgment of the treating physician, including resumption of urate-lowering therapy, if appropriate.

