9.4 Treatments

9.4.1 Treatments Administered

9.4.1.1 Methotrexate

During the MTX Run-in Period, which begins 6 weeks prior to the first dose of pegloticase, subjects with eGFR ≥ 45 mL/min/1.73 m² will inject SC MTX weekly at a starting dose of 15 mg

at Weeks -6 and Week -5 increasing to 25 mg at Week -4 and continuing weekly throughout the trial. Subjects with eGFR ≥ 30 and <45 mL/min/1.73 m² will inject SC MTX weekly at a starting dose of 10 mg at Week -6 and Week -5 increasing to 15 mg at Week -4 and continuing weekly throughout the trial. If a subject becomes unable to tolerate MTX at 25 mg doses, the folic acid dose may be increased from 1 to 2 mg/day and/or the MTX dosage may be decreased to 20 or 15 mg, but to no less than 15 mg. Subjects who cannot tolerate MTX at a minimum dose of 15 mg during the MTX Run-in Period will be considered MTX Run-in Screen Failures, regardless of their Baseline eGFR.

During the MTX Run-in Period, if a dose is missed, it should be injected as soon as it is remembered. If it is within 48 hours of the next scheduled dose, the subject will be instructed to skip the missed dose and resume at the next regularly scheduled time. If a subject misses more than 2 doses of MTX during the 6-week Run-in Period, the Principal Investigator should contact the Sponsor to discuss eligibility of the subject for enrollment in the Pegloticase + MTX Treatment Period.

During the Pegloticase + MTX Treatment Period, subjects will be instructed to inject MTX weekly on the same day each week, within 1 to 3 days prior to each pegloticase infusion (on the weeks when pegloticase is administered); however, if a subject does not do so, MTX must be injected ≥ 60 minutes prior to each pegloticase infusion. One additional weekly dose of MTX will be injected after the last pegloticase infusion for subjects who have not stopped pegloticase due to individual subject SUA discontinuation criteria. If the subject discontinues pegloticase due to the stopping rule or other reason, MTX should also be discontinued.

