9.4.11 Treatment Compliance

A dosing calendar will be provided to subjects at the Week -6 Visit for recording the MTX dose and the date, time and mg dose of each dose. The dosing calendar and MTX auto-injector should be brought to each trial visit for assessment of compliance. At the end of the trial or if the subject prematurely discontinues the trial, the subjects will return any unused or partially used trial drugs to the site. Adherence to the MTX regimen will also be recorded by the trial coordinator at trial visits in the eCRF by recording the date of each MTX dose (mg), frequency and time of each dose per calendar day. Subjects who have injected at least 80% of the protocol-specified amount of MTX will be considered compliant. Noncompliant subjects will be re-educated on compliance.

At trial visits, the subject will be asked whether folic acid, gout flare and IR prophylaxis were administered.

Pegloticase will be administered at the trial site by trained personnel. The date and time of infusion start and stop and the stop and start time of the flush will be recorded.

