9.5.4.1.7 Medication Error and Overdose

An overdose is defined as a known deliberate or accidental administration of investigational drug to or by a trial subject, at a dose above that which is assigned to that individual subject according to the trial protocol.

All cases of medication errors and overdose (with or without associated AEs) will be documented on the eCRF in order to capture this important safety information consistently in the database. AEs associated with an overdose and SAEs of overdose are to be reported according to the procedures outlined in [Section 9.5.4.1.2](#) and [Section 9.5.4.1.5](#), respectively.

In the event of drug overdose, the subject is to be treated as appropriate.

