- Obtain blood samples for hematology and clinical chemistry analysis and eGFR calculation (calculated by the central laboratory).
- Obtain a urine sample for albumin:creatinine ratio.
- Provide dosing calendar for subjects to record the date and time they inject MTX. Additional calendar pages will be provided at future visits as needed.
- Assess MTX compliance/reconciliation.
- Re-dispense MTX.
- If subject has not injected MTX within the previous 1 to 3 days, administer MTX ≥ 60 minutes prior to pegloticase infusion.
- Ask Yes/No question regarding folic acid, gout flare prophylaxis and IR prophylaxis compliance.
- Fill gout prophylaxis, IR prophylaxis and folic acid prescriptions, as needed.
- Obtain blood samples for [CCI](#) [REDACTED].
- Obtain blood sample for [CCI](#) [REDACTED] analysis.
- Administer IR prophylaxis (see [Section 9.4.1.5](#)).
- Inquire about AEs and concomitant medication use.

INFUSION: Following completion of the above procedures, administer the 2nd dose of pegloticase and record date, volume and duration of infusion and start/stop (IV infusion 120 \pm 15 minutes) times of dosing and the start/stop times of the 10 ml flush.

Post-infusion Week 2

At Week 2, the following assessments will be performed after the pegloticase infusion.

- Record vital signs (blood pressure, respiratory rate, temperature and heart rate) any time after the end of the infusion, but prior to subject's discharge/release from the site (see Section 9.5.4.4).
- Obtain blood sample for CCI after the end of the infusion, prior to discharge from the site.
- Obtain blood sample to evaluate sUA (only 1 sample for central laboratory) on the 1st day (~24 hours) after the pegloticase infusion.
- Obtain blood sample to evaluate sUA (only 1 sample for central laboratory) on the 4th day (~96 hours) after the pegloticase infusion.
- Obtain blood sample to evaluate sUA (only 1 sample for central laboratory) on the 7th day (~168 hours) after the pegloticase infusion.
- Obtain blood sample to evaluate sUA (only 1 sample for central laboratory) on the 10th day (~240 hours) after the pegloticase infusion.

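### The MTX line at infusion visits depends on time since the last injection, not on whether a weekly dose is due, so at some late visits it can add a dose if the fixed weekday is kept

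*Protocol*

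**What the plan says.** The Schedule of Assessments (Protocol 2.1) sets MTX dosing at "Once weekly from Week -6 to Week 23 Visit, inclusive", and in the extension at "Once weekly from Week 24 to the Week 47, inclusive". Sections 9.1 and 9.4.1.1 add the anchor: "subjects will be instructed to inject MTX weekly on the same day each week, within 1 to 3 days prior to each pegloticase infusion". The same schedule allows visits to move by 3 days either way, and Section 9.1 ties later visits to the Day 1 date.

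There is a fallback for subjects who miss that timing. Footnote 13 of the schedule reads "however, if a subject does not do so, MTX must be injected", followed by a minimum of 60 minutes before the infusion. Sections 9.1 and 9.4.1.1 carry the same sentence.

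The visit lists in Sections 9.5.8.3 and 9.5.8.5 turn this into a checklist item: "If subject has not injected MTX within the previous 1 to 3 days, administer MTX". It appears at Day 1 and at every infusion visit from Week 2 to Week 46. It also appears at Week 23, which has no infusion.

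The only missed-dose and skip rule is limited to the Run-in: "During the MTX Run-in Period, if a dose is missed, it should be injected as soon as it is remembered", unless the next scheduled dose is within 48 hours.

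**The concern.** The checklist item and the weekly regimen ask different questions. The regimen asks whether this week's dose has been taken. The checklist asks whether a dose was taken in the last 1 to 3 days. At an on-time visit the two agree for an adherent subject. At a late visit they can disagree: the subject has injected as told, yet the line still calls for MTX.

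A delay after injection is foreseeable. Section 9.4.6.3.2.1 lets an infusion be held or delayed for an adverse event, and Section 9.5.1.1 wants a uric acid result before infusing.

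The stake is MTX safety and consistency between sites. The protocol doses MTX by eGFR (Section 7.3.2) and cuts or stops it for cytopenia, raised liver enzymes or symptoms (Table 9.2). Section 9.5.4.1.7 defines overdose as administration "at a dose above that which is assigned to that individual subject according to the trial protocol". With two protocol texts assigning different things, one site could give the dose as instructed while another would record the same act as a medication error.

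**Working it through.** **Inputs.** Lead k = 1, 2 or 3 days from the fixed MTX weekday to the planned infusion (9.1, 9.4.1.1). Delay s = 1, 2 or 3 days (2.1). MTX interval 7 days. Target dose 25 mg, or 15 mg for eGFR 30 to <45 (9.4.1.1).

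**Check on the calendar.** The one dose count that the plan states is 6 doses in the 6-week Run-in (Synopsis, Duration of Treatment and Follow-up). A fixed weekday at k = 1, 2 or 3 gives 42 / 7 = 6 doses in the 42 days before Day 1 in each case, so the weekly model reproduces it.

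**Days since the last dose at a late visit.** Gap g = k + s. The line is triggered when g > 3 (marked *).

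| Delay s | k = 1 | k = 2 | k = 3 |
|---|---|---|---|
| 1 | 2 | 3 | 4* |
| 2 | 3 | 4* | 5* |
| 3 | 4* | 5* | 6* |

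Six of nine cells trigger: one of three at a 1-day delay, two of three at 2 days, all three at 3 days. The gap is 4 days in three cells, 5 in two and 6 in one. The next fixed-weekday dose is due 7 − g = 3, 2 or 1 days after the visit.

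**Example.** The Week 2 visit is planned for Day 15 with k = 2, so MTX is taken on Day 13. The visit is held on Day 18 (s = 3), g = 5, and the line calls for a dose. The next weekly dose is due on Day 20. If all are taken, the subject has doses on Days 13, 18 and 20: three in 8 days instead of two. At 25 mg that is 50 mg instead of 25 mg over Days 13 to 19.

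**Effect on the treatment-period total.** With k of 1 to 3, the dose belonging to the Day 1 infusion falls in the Run-in. Later doses fall 7j − k days after Day 1. The last is the single weekly dose after the Week 22 infusion (j = 23), so 23 doses are scheduled. One additional dose, with no dose reductions, gives:

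- 25 mg: 23 × 25 = 575 mg becomes 24 × 25 = 600 mg.
- 15 mg: 23 × 15 = 345 mg becomes 24 × 15 = 360 mg.
- Ratio: 24 / 23 = 1.043, or 104.3% of schedule.

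**What the summaries would show.** The compliance rule is "Subjects who have injected at least 80% of the protocol-specified amount of MTX will be considered compliant", a floor with no ceiling, so 104.3% passes. The average dose in SAP 14.1 is total mg over doses taken: 600 / 24 = 25 mg and 360 / 24 = 15 mg, unchanged. Total mg does change. So does the number of doses, which the opening sentence of SAP 14.1 lists as an exposure summary, although the MTX bullets do not repeat it.

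**Early visits.** The line also triggers before the due dose in 3 of the 9 early combinations: (k, days early) = (1, 2), (1, 3) and (2, 3). The last dose is then 6, 5 and 6 days old, with the next due in 1, 2 and 1 days. Here too, whether the visit dose replaces the coming one is left unstated.

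**The case against.** The strongest reply is that the treatment sections already mean one dose per week. They instruct weekly injection on one weekday, and the fallback opens with a subject who has not done so, which does not describe an adherent subject at a late visit. MTX reconciliation comes before this line in the visit list. Where a further dose is wanted, after the last infusion, the protocol asks for it outright. This stands as the more natural reading, and many sites would probably withhold the dose. It does not remove the conflict, because no treatment-period sentence limits the line to a dose still due. At Week 23 pre-infusion timing cannot explain the line at all.

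The second reply is that the visit dose is extra only if the next fixed-weekday dose is also taken; otherwise it is simply early and the total is unchanged. That is correct, and the 600 and 360 mg totals depend on it. Keeping the weekday is what Sections 9.1 and 9.4.1.1 instruct, but the protocol does not say which applies after a visit dose.

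A reader might also infer that an extra dose would go unnoticed. The documents do not support that. Auto-injectors are logged by subject (9.4.5), every dose is entered in the eCRF with date, time and mg (9.4.11), and incorrect dosing is an example of a major deviation (SAP 9.2). Only the 80% floor and the average mg per dose are blind to it.

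**Conclusion.** The point holds as a minor safety correction. Read literally, the line calls for MTX in 6 of 9 in-window late combinations although the subject has already injected as scheduled. If the fixed weekday is then kept, each occurrence adds one dose of 25 or 15 mg, 104.3% of the 23 scheduled doses.

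This rests on four conditions: the delay arises after the injection, the site follows the checklist line over the weekly rule, the next weekly dose is not replaced, and dosing is at target. Six of nine is a count of combinations, not a probability; the documents give no frequency for late visits.

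Two stronger readings do not follow. Not every late visit triggers the line: with a 1-day lead the visit must be 3 days late. Nor does the protocol clearly order double dosing; it leaves two instructions unreconciled. The primary analysis, sample size and error rate are unaffected.

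**What to change.** Reword the visit line to: *If this week's scheduled MTX dose has not yet been taken, administer it at least 60 minutes prior to pegloticase infusion; do not give a second dose if it was already injected.* State that a dose given at the visit replaces that week's scheduled dose, and define this week's dose as the one attached to the planned infusion, so that early and late visits are told apart. Apply the same condition in the Synopsis (Trial Design and Dose Regimen), footnote 13 of Section 2.1, Sections 9.1 and 9.4.1.1, and Week 23 (Section 9.5.8.3.14, without the 60-minute clause).

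Under this wording none of the nine late combinations adds a dose. The cost is one clause by amendment or site memo, with no new data or visits. The downside is that in the six affected combinations MTX falls 4 to 6 days before the infusion instead of 1 to 3. If the sponsor's clinical team prefers a further dose to that gap, the protocol should say so outright and state what happens to the next weekly dose.

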9.5.8.3.15 Week 24/1st Infusion of Optional Pegloticase + MTX Extension Period

Week 24 is the final visit of the Pegloticase + MTX Treatment Period. Subjects who may not gain further benefit beyond 12 infusions based on the Principal Investigator's judgement and decide to complete the study at Week 24 (see [Section 9.5.1.1](#)) or who discontinue treatment prior to Week 22 will complete the End of Pegloticase Visit (see [Section 9.5.8.4](#)). Trial drug is not administered for subjects who may not gain further benefit beyond 12 infusions based on the Principal Investigator's judgement.

For subjects who may gain further benefit beyond 12 infusions and elect to receive trial drug, the infusion will be performed at Week 24.

Pre-infusion Week 24

At Week 24, subjects will return to the clinic for the following assessments prior to the 13th dose of pegloticase.

- Obtain 2 blood samples for measurement of sUA within 48 hours prior to the Week 14 pegloticase infusion. One sample will be tested for sUA at the site's local laboratory and 1 sample will be shipped to the central laboratory for testing. The local laboratory or central laboratory pre-infusion sUA results should be reported prior to pegloticase infusion. Note: It is allowable for the local and central laboratory sUA samples to be drawn on different days or times so long as both samples are drawn within 48 hours prior to the infusion and the results of at least 1 sample are available prior to the infusion (see [Section 9.5.1.1](#)).
- Perform a targeted physical examination (at a minimum this should include heart, lungs and abdominal examination).
- Principal Investigator review of subject clinical status and treatment goals.
- Document gout flares and intensity.
- Record vital signs (blood pressure, respiratory rate, temperature and heart rate) (see [Section 9.5.4.4](#)).
- Record weight.
- Obtain a urine sample for pregnancy testing from female subjects of childbearing potential.

- Obtain blood samples for hematology, clinical chemistry and hs-CRP analysis and eGFR calculation (calculated by the central laboratory).
- Obtain a urine sample for albumin:creatinine ratio.
- **CCI** [REDACTED].
- Administer HAQ-DI, **CCI** [REDACTED]
- Record **CCI** [REDACTED].
- Obtain optional serum and urine samples from subjects who consent for future analysis.
- Provide dosing calendar for subjects to record the date and time they inject MTX. Additional calendar pages will be provided at future visits as needed.
- Assess MTX compliance/reconciliation.
- Re-dispense MTX.
- If subject has not injected MTX within the previous 1 to 3 days, administer MTX ≥ 60 minutes prior to pegloticase infusion.
- Ask Yes/No question regarding folic acid, gout flare prophylaxis and IR prophylaxis compliance.
- Fill gout prophylaxis, IR prophylaxis and folic acid prescriptions, as needed.
- Obtain blood samples for **CCI** [REDACTED].
- Obtain blood sample for **CCI** [REDACTED].
- Obtain blood samples for **CCI** [REDACTED] analysis.
- Administer IR prophylaxis (see [Section 9.4.1.5](#)).
- A DECT scan will be obtained. DECT may be completed within ± 10 days of the scheduled visit.
- Inquire about AEs and concomitant medication use.

INFUSION: Following completion of the above procedures, administer the 13th dose of pegloticase and record date, volume and duration of infusion and start/stop (IV infusion 120 ± 15 minutes) times of dosing and the start/stop times of the 10 ml flush.

Post-infusion Week 24

At Week 24, the following assessment will be performed after the pegloticase infusion (for subjects who may gain further benefit with additional pegloticase treatment beyond 12 infusions based on the Principal Investigator's judgement).

- Record vital signs (blood pressure, respiratory rate, temperature and heart rate) any time after the end of the infusion, but prior to subject's discharge/release from the site (see [Section 9.5.4.4](#)).

